15.0 Risks to Subjects*

- 15.1 The common side effects of ropivacaine (the numbing medication used in the nerve blocks) are injection site burning or pain and prickly feeling as the block wears off. Occasional side effects of ropivacaine are ear ringing, metallic taste, and drowsiness. Rare side effects of ropivacaine are seizures, unconsciousness, respiratory arrest, low blood pressure, irregular heartbeat, cardiac arrest, and allergic reactions including anaphylaxis. There is also potential risk for loss of confidentiality.
- 15.2 Subjects and their families will be approached about the study and consented in a private room in the pre-op area by a member of the research team. The information collected will be limited to that which is required to achieve the objectives of the study and will not be shared with anyone not directly involved in the study. Subjects will be informed of their right to refuse to participate. Subject PHI will be stored in a locked cabinet, and will be stored and maintained in password protected computer files.

16.0 Potential Benefits to Subjects*

16.1 No direct benefit to the subject.

17.0 Data Management* and Confidentiality

17.1 Continuous outcomes will be compared between groups using 2sample t-test or rank-sum tests according to the normality of the distribution (checked by the Shapiro-Wilk test). Categorical outcomes will be compared between groups using Chi-square or Fisher's exact tests, according to cell size.

- 17.2 Research records will be stored in a locked cabinet and password protected computer. Only certified research personnel will be given access to identifiable subject information
- 17.3 Following publication of study results, research records will be stored for a period of 3-5 years and then will be destroyed by placing in a secure shredding bin.

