5.0 Study Intervention/Investigational Agent

5.1 Study subjects will receive up to 20 mL of 0.5% ropivacaine with epinephrine 1:200,000 and 0.2 mg/ml of dexamethasone for FNB and up to 20 mL of 0.5% ropivacaine with epinephrine 1:200,000 and 0.2 mg/ml of dexamethasone for sciatic nerve block under ultrasound guidance or posterior knee capsular infiltration under ultrasound guidance (IPACK), the total dose not to exceed 3 mg/kg of ropivacaine.

5.2 Both the FNB and sciatic nerve blocks are considered standard of care at NCH. The IPACK is not currently performed at NCH.

6.0 **Procedures Involved***

- Following informed consent, patients will be randomized into one of 6.1 the two groups. Intraoperative anesthetic care will not vary from our usual practice. Patients requiring preoperative anxiolysis will receive oral midazolam (0.3-0.5 mg/kg, maximum 20 mg) 30 minutes prior surgery or intravenous midazolam (0.05 mg/kg, maximum 2 mg) prior to transport to the operating room. Standard American Society of Anesthesiologists' monitors will be placed. Once in the operating room, anesthesia will be induced by the intravenous or inhalational route as clinically indicated. All subjects will receive propofol (2-3 mg/kg) and fentanyl (2µg/kg). Following the induction of anesthesia, an appropriately sized laryngeal mask airway (LMA) will be placed. After the regional anesthesia time out, patients will receive the block based on the group assigned from a randomization list created by www.sealedenvelope.com. The time from the initiation of the timeout for the block until the patient has been returned to the surgical position will be noted.
- 6.2 The following demographic and surgical parameters will also be collected and recorded: patient age, gender, race/ethnicity, height, weight, ASA status, primary diagnosis, list of comorbidities, procedure date and duration, admission status, intraoperative medications and postoperative medications, PACU arrival and discharge times, discharge destination, pain scores (including recorded time), regional anesthetic time and dose, postoperative opioids consumed and time of hospital admission and discharge.

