- 6.3 Group 1: Patients will receive up to 20 mL of 0.5% ropivacaine with epinephrine 1:200,000 and 0.2 mg/ml of dexamethasone for FNB and up to 20 mL of 0.5% ropivacaine with epinephrine 1:200,000 and 0.2 mg/ml of dexamethasone for sciatic nerve block under ultrasound guidance, the total dose not to exceed 3 mg/kg of ropivacaine (total volume 1.5 mL/kg of 0.2% ropivacaine). For patients who weigh less than 30 kg, the volume of the local anesthetic will be reduced to keep the total dose at \leq 3 mg/kg.

Group 2: Patients will receive up to 20 mL of 0.5% ropivacaine with epinephrine 1:200,000 and 0.2 mg/ml of dexamethasone for FNB and up to 20 mL of 0.5% ropivacaine with epinephrine 1:200,000 and 0.2 mg/ml of dexamethasone for posterior knee capsular infiltration under ultrasound guidance (IPACK), the total dose not to exceed 3 mg/kg of ropivacaine. For patients who weigh less than 30 kg, the volume of the local anesthetic will be reduced as needed to keep the total dose at \leq 3 mg/kg.

- 6.4 For intraoperative increases in heart rate or systolic blood pressure $\geq 20\%$ above the baseline, fentanyl (1 µg/kg) will be administered every 5 minutes until the heart rate is below this threshold. Prophylaxis for postoperative nausea and vomiting will include ondansetron (0.1-0.15, maximum 4 mg). At the conclusion of the procedure, all patients will receive ketorolac (0.5 mg/kg, maximum 30 mg).
- 6.5 Patients experiencing severe pain with VAS scores >7 at the surgical site will be considered as failed FNB or sciatic nerve block and will be withdrawn from the study. In the postoperative care unit, the nursing staff will be blinded to which group the patient was assigned to, reducing bias. Fentanyl (1 μ g/kg, maximum 50 μ g) will be administered every 5-10 minutes as needed until the patient's visual analogue score (VAS) score is \leq 4. VAS will be evaluated every hour until discharge. When the patients are ready for discharge and tolerating oral intake, analgesia will be changed to hydrocodone with acetaminophen, 1 tablet by mouth if needed, prior to discharge home.

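### The valid unadjusted tests in 17.1 make no use of recorded body weight, which the dosing rules tie to maximum block dose and intraoperative fentanyl; adjusting for it offers a modest, cheap gain

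*Combined protocol and SAP*

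**What the plan says.** Section 17.1 gives the whole analysis of continuous outcomes: "Continuous outcomes will be compared between groups using 2sample t-test or rank-sum tests", with a Shapiro-Wilk check of normality deciding which. Categorical outcomes get chi-square or Fisher's exact tests. No covariate, regression model or stratified randomisation appears anywhere.

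Section 6.2 lists the baseline data to be collected, including "patient age, gender, race/ethnicity, height, weight, ASA status". Section 10.2 admits ages 10 to 21.

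Weight enters the dosing rules as follows:

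- **Block (5.1, 6.3).** Up to 20 mL of 0.5% ropivacaine at each of two sites, with dexamethasone 0.2 mg/mL, and "the total dose not to exceed 3 mg/kg of ropivacaine". Section 6.3 adds: "For patients who weigh less than 30 kg, the volume of the local anesthetic will be reduced".
- **Intraoperative fentanyl (6.1, 6.4).** 2 µg/kg at induction, then 1 µg/kg boluses that "will be administered every 5 minutes until the heart rate is below this threshold". No maximum is stated.
- **PACU fentanyl (6.5).** 1 µg/kg up to 50 µg, which "will be administered every 5-10 minutes as needed until the patient's visual analogue score (VAS) score is" at most 4.
- **Home opioid (6.6).** One tablet per dose at any weight.

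Section 12.2 sizes the trial on maximal POD0 pain, using an unadjusted one-tailed t-test for non-inferiority with a 1-point margin and SD 1.1. Section 4.2 makes the intraoperative fentanyl requirement an endpoint but does not say whether it is analysed in µg or µg/kg.

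**The concern.** Patients aged 10 to 21 can be expected to differ widely in weight. If weight predicts an outcome, an unadjusted comparison leaves that variation in the error term. A chance weight imbalance between two arms of 25 then moves the estimate as well. Weight is fixed before randomisation and already collected, so a model that includes it keeps the randomised comparison valid and may narrow the interval that is set against the 1-point margin.

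For intraoperative fentanyl the link is close to mechanical. Two patients who need the same number of per-kg boluses have different totals in µg only because they weigh different amounts.

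**Working it through.** **1. The plan's own figure.** Inputs from 12.2: margin 1, SD 1.1, true difference 0, one-sided α 0.05. The noncentrality is 1/(1.1·√(2/n)).

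- n = 21: power 89.4%.
- n = 22: 1/(1.1·√(2/22)) = 3.01 on 42 df, power 90.7%.
- n = 25: 1/(1.1·√(2/25)) = 3.21 on 48 df, power 93.6%.

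So 22 per group is the smallest size that reaches 90%. The stated figure reproduces, and it already assumes an unadjusted test.

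**2. Weight and maximum block dose.** Two sites × 20 mL × 5 mg/mL = 200 mg, and 200/3 = 66.7 kg. Below that weight the cap limits the dose. Maximum volume is min(40, 3·kg/5) mL:

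| Weight (kg) | Max ropivacaine (mg) | Max volume (mL) | Dexamethasone at that volume (mg) |
|---|---|---|---|
| 30 | 90 | 18 | 3.6 |
| 40 | 120 | 24 | 4.8 |
| 50 | 150 | 30 | 6.0 |
| 60 | 180 | 36 | 7.2 |
| 66.7 and above | 200 | 40 | 8.0 |

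Section 6.3 describes a reduction only below 30 kg, whereas the cap arithmetic requires one below 66.7 kg. For Group 1 it also equates the cap with 1.5 mL/kg of a 0.2% solution (1.5 × 2 = 3 mg/kg), although the solution specified is 0.5%, for which 3 mg/kg is 3/5 = 0.6 mL/kg. These statements disagree. If the 30 kg rule is the one applied, maximum volume hardly varies with weight in most of this population.

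**3. Effect of adjusting the primary outcome for weight.** Let R² be the share of within-arm variance that weight explains. The documents give no value, so 0 to 20% is an assumed range. The residual SD is 1.1·√(1−R²), one degree of freedom is lost (47 left), and the variance of the difference is inflated by 1 + 1/46 for estimating the slope. The distance to the margin is 1 minus the true difference. Section 12.2 takes the true difference as 0; 0.25 is an added assumption.

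| Analysis, 25 per arm | Residual SD | Power, true diff. 0 | Power, true diff. 0.25 | One-sided 95% half-width |
|---|---|---|---|---|
| Unadjusted | 1.10 | 93.6% | 76.8% | 0.52 |
| Weight, R² = 0 | 1.10 | 93.2% | 76.0% | 0.53 |
| Weight, R² = 5% | 1.07 | 94.2% | 77.8% | 0.51 |
| Weight, R² = 10% | 1.04 | 95.1% | 79.7% | 0.50 |
| Weight, R² = 20% | 0.98 | 96.8% | 83.7% | 0.47 |

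Break-even is near (1−R²)·(47/46) = 1, that is R² = 1/47 ≈ 2%. Adding age as a second covariate (46 df, inflation 1 + 2/45) gives about 93.7% at R² = 5% and true difference 0, so nearly all of the gain goes.

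**4. Chance imbalance.** The standard error of the difference in mean weight is √(2/25) = 0.28 weight SDs. At R² = 10% (r = 0.32), an imbalance of that size shifts the unadjusted pain difference by 0.28 × 0.32 × 1.1 ≈ 0.10 points.

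**5. Fentanyl units.** Simulated trials with assumed inputs: weight 62 ± 16 kg, Poisson bolus counts with means 1.5 and 2.5 that are independent of weight, 25 per arm, two-sided rank-sum test. For boluses alone, power is about 66% in µg/kg against about 59 to 61% in raw µg. If the 2 µg/kg induction dose is counted, it is about 67% against 47 to 48%.

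**The case against.** The strongest reply is that nothing in 17.1 is wrong. Two-sample tests after randomisation are valid, the trial was sized on one, and at 25 per arm it keeps 93.6% power under its own assumptions. That stands. A reader might infer that leaving weight out biases the comparison or makes the trial underpowered; the documents support neither.

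A reader might also infer that weight drives all the pain, duration and opioid outcomes. The documents do not show this either:

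- No correlation between weight and any outcome is given. For pain the link is only plausible, and PACU fentanyl is titrated to the pain score.
- The block volumes are upper limits, flat from 66.7 kg, and depend on which of two conflicting rules is followed. That a 40 kg patient receives 24 mL rather than 40 mL follows only if the cap governs and the maximum is given.
- PACU boluses scale with weight only below 50 kg. Home tablets are not scaled at all, and block time has no stated link to weight.

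Nor is adjustment free. The large-sample formula 1/(1−R²) suggests a gain worth 5, 11 or 25% more patients at R² of 5, 10 or 20%, but it omits the cost of estimating the slope. With that cost included the gains are those in the table, and there is a small loss if weight is not prognostic.

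The objection does not remove the point. The possible loss is under one percentage point of power, the possible gain is larger, and for intraoperative fentanyl in µg the link follows from the dosing rule itself.

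**Conclusion.** The point holds as a modest gain in efficiency. The plan's tests are valid and its sample size is reproducible, but they leave unused a recorded baseline value that the plan's own rules connect to maximum block dose and intraoperative fentanyl.

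For maximal POD0 pain at 25 per arm and SD 1.1, weight adjustment changes power by −0.4 points at R² = 0 and by +0.6, +1.5 or +3.2 points at R² of 5, 10 or 20% when the true difference is 0. At an assumed true difference of 0.25 the changes are −0.8, +1.0, +2.9 and +6.9 points. All of these rest on assumed R² values. The most concrete gain is in the fentanyl comparison, where the choice of unit alone is worth about 5 to 7 points of power under the assumed inputs for boluses alone.

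The block-dose part of the argument depends on the cap being the operative rule. It weakens if the 30 kg rule is applied; the fentanyl part does not.

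**What to change.** In 17.1, before any outcome data are seen by arm:

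1. Prespecify a linear model of maximal POD0 pain on arm plus baseline weight. Report the adjusted difference with its one-sided 95% confidence limit against the 1-point margin, and show the unadjusted result beside it.
2. Use the same model for block duration.
3. Adjust for weight only. Leave out age, which uses up most of a small gain, and delivered volume, which is determined after randomisation.
4. Analyse intraoperative fentanyl in µg/kg, and state whether the induction dose is counted.
5. Leave block time and home tablet counts unadjusted.

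Separately, reconcile the 30 kg volume rule, the 3 mg/kg cap and the 0.2% volume equivalent in 6.3, so that it is clear how block volume depends on weight.

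The analysis changes cost a few sentences of SAP wording and one of 48 degrees of freedom. They need no extra data or patients, and lose under one point of power if weight turns out not to be prognostic.

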1.0 Study Summary

Study Title	Comparison of postoperative analgesic efficacy of femoral	
	nerve block with IPACK versus femoral and popliteal sciatic	
	nerve block in patients undergoing arthroscopic anterior	
	cruciate ligament reconstruction.	
Study Design	Prospective study	
Primary Objective	The primary objective of the study is to compare the	
	analgesic efficacy of FNB with IPACK versus FNB with	
	sciatic nerve block in patients undergoing ACL repair by	
	monitoring postoperative pain scores.	
Secondary	The secondary objective is to show a decreased incidence of	
Objective(s)	adverse effects including motor blockade with IPACK	
	compared to sciatic nerve block and to demonstrate that it is	
	technically less challenging by showing a decreased time	
	required for performance of the block.	
Research	Patients will receive up to 20 mL of 0.5 % ropivacaine with	
Intervention(s)/	epinephrine 1:200,000 and 0.2 mg/ml of dexamethasone for	
Investigational	FNB-AC and up to 20 mL of 0.5% ropivacaine with	
Agent(s)	epinephrine 1:200,000 and 0.2 mg/ml of dexamethasone for	
	sciatic nerve block or posterior knee capsular infiltration.	
IND/IDE #	N/A	
Study Population	Patients undergoing elective anterior cruciate ligament	
	reconstruction.	
Sample Size	50	
Study Duration for	Total of 2 weeks.	
individual		
participants		
Study Specific	IPACK – infiltration of the posterior knee capsule	
Abbreviations/	FNB - Femoral nerve block	
Definitions	PACU – post-anesthesia care unit	
	POD – post-op day	

2.0 **Objectives**

- 2.1 The primary objective of the study is to compare the analgesic efficacy of FNB with IPACK versus FNB with sciatic nerve block in patients undergoing ACL repair by monitoring postoperative pain scores.
- 2.2 The secondary objective is to show a decreased incidence of adverse effects including motor blockade with IPACK compared to sciatic nerve block and to demonstrate that it is technically less challenging by showing a decreased time required for performance of the block.
- 2.3 We hypothesize that FNB with IPACK provides the same analgesic efficacy as FNB with sciatic block while avoiding the motor blockade associated with sciatic nerve block.

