4.0 Study Endpoints

- 4.1 The time for performance of the block (FNB plus sciatic versus FNB plus IPACK).
- 4.2 Intraoperative opioid (fentanyl) and inhalational anesthetic agent (sevoflurane) requirements.
- 4.3 Pain scores and opioid requirements in the PACU.
- 4.4 Degree of sensory and motor block in phase I (PACU) and phase 2 recovery.
- 4.5 Post-discharge opioid requirements and pain scores (pain diary).
- 4.6 Duration of subjective postoperative sensory and motor blockade.

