- 6.6 Patients will be discharged home with postoperative pain medication to include hydrocodone with acetaminophen. Parents will be instructed to administer one tablet every 4 hours as needed when the VAS score is greater than 4. If the patient does not tolerate hydrocodone, the patient will be given the option for ibuprofen 10 mg/kg every 6 hours. Caregivers will be given a diary to record the amount of pain medication consumed, pain scores (every 4-6 hours), and the duration of motor block as reported by the patient. On postoperative day 1(or 2 for a later discharge), a member of the study team will call to collect the information for a total of 24 hours following hospital discharge. The study investigator will also contact the patients 2 weeks after the procedure to assess for any adverse events not detected during the initial data collection.

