12.0 Local Number of Subjects

- 12.1 50
- 12.2 Sample size will be determined according to previous studies in adults. Abdallah et al. described the non-inferiority of the IPACK block over 24 hours postoperatively, while Kim et al. described superiority of IPACK with respect to pain scores at rest and ambulation, as well as opioid consumption, over postoperative days 0-1. With the greatest pain observed on POD0, our study will be powered for comparing the maximal pain score on POD0 between the 2 groups. Based on the data presented by Abdallah et al., we anticipate that pain scores over POD0 would differ by no more than 1 point between the groups, on a 0-10 scale. Based on the data presented by Kim et al., we hypothesize a standard deviation of pain scores of 1.1. Following Abdallah et al, our study will be powered for a test of IPACK non-inferiority, such that the null hypothesis will

be rejected if pain scores in the IPACK group are >1 point greater than in the control group. Under these assumptions, an unpaired onetailed t-test would attain 90% power for rejecting the null hypothesis at a 95% confidence level when at least 22 patients are enrolled in each group. We propose enrolling a total of 50 patients to account for non-normal distribution of the primary outcome; protocol violations resulting in subject exclusion; and missing data.

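### Block duration (endpoint 4.6) is collected only to 24 hours after discharge and analysed by t-test or rank-sum, with no rule for blocks still unresolved at that point

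*Combined protocol and SAP*

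**What the plan says.** - Section 4.6 lists as an endpoint "Duration of subjective postoperative sensory and motor blockade".
- Section 6.6 has caregivers keep a diary that includes "the duration of motor block as reported by the patient". Sensory block is not among the diary items. On postoperative day 1, or day 2 after a later discharge, "a member of the study team will call to collect the information for a total of 24 hours following hospital discharge".
- Section 6.6 also plans a contact two weeks after the procedure. Its stated purpose is "to assess for any adverse events not detected during the initial data collection". A block end time is not mentioned.
- Section 17.1 covers every continuous outcome in one sentence: "Continuous outcomes will be compared between groups using 2sample t-test or rank-sum tests according to the normality of the distribution". No time-to-event method is named, and no section says how to record or analyse a block still present when collection ends.
- Objective 2.2 is to "show a decreased incidence of adverse effects including motor blockade with IPACK compared to sciatic nerve block", and to show a shorter time to perform the block. It does not name duration of blockade.

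**The concern.** A duration is known only if its end is observed. Under 6.6 the last contact that gathers block information covers 24 hours from discharge, so for any block that lasts longer the plan yields a lower bound and no end time. The cut-off is not a common one either. It runs from discharge, while the block starts in the operating room, so it differs between patients.

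Section 17.1 then calls for a test that needs one complete number per patient. The analyst would have to choose, with the data in hand, between entering the cut-off as if it were the duration and leaving the patient out. Both choices remove more from the arm with the longer blocks. If that is the sciatic arm, the reported difference in duration is too small. The missing end time cannot be recovered later unless someone asks for it.

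**Working it through.** **1. The plan's own figure.** The plan gives no figure for block duration. Its only sample-size figure, 22 per group, is for the primary pain score. Section 12.2 states that "an unpaired onetailed t-test would attain 90% power for rejecting the null hypothesis". Inputs from 12.2 are margin 1, SD 1.1, one-sided alpha 0.05 and power 0.90. I assume a true difference of 0.

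n per group = 2 × SD² × (z₀.₉₅ + z₀.₉₀)² / margin² = 2 × 1.21 × (1.645 + 1.282)² / 1 = 20.7, so 21 by the normal approximation. By the noncentral t, power is 0.894 at 21 and 0.907 at 22. The stated 22 reproduces, and nothing below changes it.

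**2. Effect on the estimated difference in duration.** All inputs here are assumptions: normal durations, a true difference of 6 h with sciatic longer, and observation ending c = 28 h after the block (24 h after discharge plus about 4 h from block to discharge). With z = (c − μ)/σ:

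- fraction censored = 1 − Φ(z)
- mean if the cut-off is entered = μΦ(z) − σφ(z) + c(1 − Φ(z))
- mean if unresolved blocks are dropped = μ − σφ(z)/Φ(z)

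Example, means 24 and 18 h, SD 6:

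- Sciatic: z = 0.667, Φ = 0.7475, φ = 0.3194. Capped mean = 17.94 − 1.92 + 7.07 = 23.09. Dropped mean = 24 − 2.56 = 21.44.
- IPACK: z = 1.667, Φ = 0.9522, φ = 0.0995. Capped mean = 17.14 − 0.60 + 1.34 = 17.88. Dropped mean = 18 − 0.63 = 17.37.
- Difference: 5.2 h capped, 4.1 h dropped.

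| Sciatic / IPACK mean, SD (h) | Censored, sciatic / IPACK | Capped difference (h) | Dropped difference (h) |
|---|---|---|---|
| 18 / 12, 6 | 5% / 0.4% | 5.9 | 5.4 |
| 20 / 14, 6 | 9% / 1% | 5.8 | 5.1 |
| 24 / 18, 6 | 25% / 5% | 5.2 | 4.1 |
| 28 / 22, 6 | 50% / 16% | 4.1 | 2.9 |
| 30 / 24, 8 | 60% / 31% | 3.3 | 2.4 |

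**3. Effect on the test.** Simulation with 25 per arm (50 in total, section 12.1), true difference 6 h, SD 6, each patient's cut-off drawn uniformly from 26 to 30 h, two-sided 0.05, 2,000 runs per row. In the capped columns each unresolved block takes its own cut-off as its value.

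| Censored, sciatic / IPACK | t, no censoring | t, capped | t, dropped | Rank-sum, capped | Rank-sum, dropped | Log-rank |
|---|---|---|---|---|---|---|
| 9% / 1% | 0.94 | 0.94 | 0.88 | 0.92 | 0.86 | 0.89 |
| 26% / 5% | 0.93 | 0.93 | 0.74 | 0.91 | 0.72 | 0.89 |
| 50% / 16% | 0.93 | 0.89 | 0.46 | 0.87 | 0.45 | 0.88 |
| 75% / 37% | 0.94 | 0.79 | 0.16 | 0.71 | 0.18 | 0.84 |

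Rank-sum power without censoring is 0.91 to 0.92 in these rows. Capping therefore distorts the estimate well before it harms the test. Dropping harms both, whichever test is used.

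**The case against.** **No figure shows that any block outlasts the window.** This stands. The documents give no expected duration, and at 18 versus 12 h the capped difference loses only 0.1 h. The bias is conditional, and may be negligible.

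**The rank-sum branch of 17.1 largely copes.** This stands for light to moderate censoring. Values piled up at a common cap tend to fail Shapiro-Wilk, which sends the comparison to a rank test that places unresolved blocks as longest. With the whole 17.1 procedure simulated at a common 28 h cap, power was 0.93 against 0.94 uncensored (24 versus 18 h, SD 6) and 0.91 against 0.93 (28 versus 22 h, SD 6), but 0.66 against 0.74 at 30 versus 24 h, SD 8. A reader might infer that the stated analysis is wrong whenever any block outlasts the window, and these results contradict that. The plan does not, however, say that unresolved blocks are kept and ranked longest. With cut-offs that differ between patients, a block unresolved at 26 h would rank below one that resolved at 27 h, although it may have lasted longer.

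**Dropping is not in the plan.** True. Section 17.1 is silent, so the dropped figures show what one available choice would cost, not what the plan prescribes.

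**The two-week contact may pick up a prolonged block.** Partly. Objective 2.2 classes motor blockade as an adverse effect, so a persistent block could be reported then, but the contact is not described as obtaining an end time.

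**Both arms receive a femoral block (6.3), and the diary records one motor-block duration, not separated by nerve.** This stands. The true contrast in 4.6 may be smaller than the assumed 6 h.

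**The bias runs against IPACK.** True if sciatic blocks last longer. It would then understate a benefit, not create one.

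**Conclusion.** The concern holds in a limited form. Endpoint 4.6 is a time to resolution with a patient-specific end of observation, and neither 6.6 nor 17.1 provides for a block that passes it. If such blocks occur and sciatic blocks last longer, the estimated difference in duration is biased towards zero. Under the assumptions shown, a true 6 h difference becomes 5.9 to 3.3 h with capping and 5.4 to 2.4 h with dropping, as sciatic-arm censoring goes from about 5% to about 60%. The direction is firm under those two conditions. The size is unknown, because every duration used is an assumption.

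A reader might infer that the secondary objective itself is compromised. The documents do not support that. Objective 2.2 concerns the incidence of adverse effects including motor blockade, and the time to perform the block. Neither that incidence measure nor the degree of block assessed in recovery (4.4) depends on the end of the diary window. The primary outcome and the 22 per group are also untouched. This is an inexpensive improvement to one listed endpoint.

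**What to change.** - **Section 6.6.** At the day 1-2 call, record whether the block has resolved and, if so, when. At the two-week contact already planned, ask for the end time of any block that was unresolved at that call.
- **Section 17.1.** Analyse duration from block completion to resolution. Blocks that still lack an end time are censored at last contact and are not dropped. Report Kaplan-Meier estimates and compare groups by the log-rank test.
- **Sections 4.6 and 6.6.** Reconcile them: the endpoint names sensory and motor block, while the diary lists only motor block.

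The cost is a question at each of two contacts already planned, a sentence on analysis, and a diary item if sensory duration is kept. There are two downsides. End times asked for at two weeks are recalled less exactly. Log-rank also has slightly less power when censoring is light: 0.89, against 0.94 for the capped t-test and 0.92 for the capped rank-sum test at 9% / 1% censoring. Under heavy censoring the order reverses: 0.84 against 0.79 and 0.71 at 75% / 37%. No change to the sample size is needed.

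### Section 17.1 does not carry the 1-point non-inferiority test of 12.2 into the analysis, and it lets Shapiro-Wilk swap the powered t-test for a rank-sum test that does not address the margin on means

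*Combined protocol and SAP*

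**What the plan says.** Section 12.2 names the outcome: "our study will be powered for comparing the maximal pain score on POD0 between the 2 groups". It expects that "pain scores over POD0 would differ by no more than 1 point between the groups, on a 0-10 scale", takes an SD of 1.1, and calls for a test of IPACK non-inferiority. On that basis "an unpaired onetailed t-test would attain 90% power for rejecting the null hypothesis at a 95% confidence level" with 22 patients per group. Total enrolment is set at 50, partly "to account for non-normal distribution of the primary outcome".

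Section 17.1 holds the whole analysis plan. Continuous outcomes are compared by "2sample t-test or rank-sum tests according to the normality of the distribution (checked by the Shapiro-Wilk test"). It does not mention non-inferiority, the margin, a one-sided test or a confidence limit, and it makes no exception for the primary outcome. It also leaves open the level of the Shapiro-Wilk test and whether it is applied per arm, to the pooled data or to residuals.

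**The concern.** The two sections do not describe the same test. An analyst who follows 17.1 literally runs an ordinary comparison against zero difference. A non-significant result could then be read as equal efficacy, which is not a non-inferiority finding.

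The rank-sum branch adds a second problem. It asks whether one arm's scores tend to be lower, not how far apart the means are. Subtracting 1 point from the IPACK scores first would build in the margin, but the result matches a test on means only if the two distributions have the same shape. A posterior block that works in most patients and fails in some gives a skewed or two-humped IPACK arm. That shape tends to trigger the switch, and the rank-sum test then discounts how bad the failures are. At stake is a false non-inferiority claim on the primary outcome.

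**Working it through.** **Inputs from 12.2.** Margin 1 point; SD 1.1; true difference 0; one-sided 5%; power 90%; 22 per group; 50 in total, so 25 per group if allocation is equal.

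**1. The plan's own figure.** Normal approximation: n = 2 × SD² × (1.645 + 1.282)² / margin² = 2 × 1.21 × 8.57 / 1 = 20.7, so 21 per group. The exact noncentral t calculation gives power 0.894 at 21, 0.907 at 22 and 0.936 at 25. The stated 22 is reproduced, and it belongs to a one-sided margin test on means. A two-sided 5% version would need 26 and does not match.

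**2. How often the switch occurs without block failures.** Simulation with 25 per arm, normal scores with SD 1.1 and clipped to 0-10, and rank-sum used if Shapiro-Wilk gives p < 0.05 in either arm (both the level and the either-arm rule are assumptions):

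| Score recorded in | Switch to rank-sum |
|---|---|
| whole points | about 95% |
| half points | about 27% |
| 0.1 points | about 10% |

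With whole numbers and SD 2.0 the range is 29-48% (means 3 to 5). With fine scoring near the floor (mean 1) it is 54-95%.

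**3. Pure 1-point shift, no failures.** The t-test against the margin passes IPACK in 5.0% of trials and the margin-shifted rank-sum in 4.8%. The switch does no harm when the shapes agree.

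**4. Minority failure, true mean difference at the margin.** Assume a share p of IPACK patients score d points higher on average. The mean difference is p × d, and the IPACK SD is √(1.1² + p(1 − p)d²):

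- p = 0.25, d = 4: difference 1.00, SD √(1.21 + 3.00) = 2.05
- p = 0.20, d = 5: difference 1.00, SD √(1.21 + 4.00) = 2.28
- p = 0.33, d = 3: difference 0.99, SD √(1.21 + 1.99) = 1.79

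Proportion of trials declaring non-inferiority, 25 per arm, 1,000 runs per setting, shown as whole-number / fine scoring:

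| Failure pattern | Control mean | Switch occurs | t-test against margin | Two-stage, margin-shifted |
|---|---|---|---|---|
| 25% by 4 | 3 | 94 / 55% | 6.8 / 7.7% | 18.4 / 17.9% |
| 20% by 5 | 2 | 99 / 92% | 8.4 / 7.6% | 30.3 / 30.4% |
| 20% by 5 | 3 | 98 / 88% | 8.1 / 6.5% | 28.4 / 31.9% |
| 33% by 3 | 2 | 92 / 23% | 5.4 / 6.8% | 9.4 / 10.5% |

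Simulation error is about 1 to 1.5 percentage points. Larger runs (3,000 to 6,000 trials) of the 4- and 5-point patterns gave 16-30% for the two-stage rule. With equal arms the pooled and Welch t statistics are the same and differ only in degrees of freedom.

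**5. The rank-sum test as written in 17.1 (no margin, two-sided).** In the 4- and 5-point patterns it is non-significant in 67-79% of trials, although the true mean difference is about 1.0.

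**6. Scores above 7 removed.** If the withdrawal in 6.5 and 14.1 means that these scores leave the analysis (whole-number scores, 25 per arm, four failure patterns), the analysed mean difference falls to 0.28-0.88. The t-test then passes IPACK in 11-59% of trials and the two-stage rule in 24-68%.

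**The case against.** A reader might infer that the switch will usually happen. The documents do not support that. The scale is 0-10 and the instrument is called a VAS, but no resolution is given, and at 0.1-point scoring without failures the switch occurs in only about 10% of trials.

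A reader might also take a false-pass rate near 30% as a property of the plan. It is not. The failure shares and sizes are assumptions, and they raise the IPACK SD to about 2 against the planned 1.1. Inflation is small for 33% failing by 3 points and absent under a pure shift. The rates also belong to a margin-shifted rank-sum test, which is the charitable reading of 17.1 and appears nowhere in the plan.

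It can fairly be said that 12.2 foresees non-normality and adds patients for it, that rank-sum tests are common for bounded pain scores, and that 12.2 never uses the word mean. With equal arms of 25, the shifted rank-sum has about 92% power, so the extra patients do protect power. They do not make a rank-sum test answer a question about a 1-point mean difference. That the target is the mean is inferred from the t-test and the SD used in 12.2.

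Finally, dropping scores above 7 can inflate false passes under either test. That stands as a separate problem, which this change does not cure.

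**Conclusion.** The point holds in conditional form. What is certain from the text is that 17.1 omits the margin and the one-sided test in both branches and applies a data-driven choice of test to the primary outcome, so following it need not answer the question that 12.2 powers. The size of the harm depends on how pain is distributed. There is none under a pure shift. With the true mean difference at the margin, a margin-shifted two-stage rule gives about 8-10% false passes if 33% of IPACK blocks fail by 3 points, and 16-30% if 20-25% fail by 4-5 points. A t-test against the margin gives about 5-7% and 6-8% in those same patterns, against a nominal 5%. The 4- and 5-point result persists at fine scoring, so it does not rest on whole-number scores. All these rates assume 25 per arm, SD 1.1 within each component, Shapiro-Wilk at 0.05 in either arm, and every score kept in the analysis.

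**What to change.** In 17.1, exempt the primary outcome from the normality rule and state: the mean difference in maximal POD0 pain (IPACK minus sciatic) is estimated with a one-sided 95% upper confidence limit by Welch's t method, and non-inferiority is declared if that limit is below 1 point, whatever Shapiro-Wilk shows. Report a bootstrap or permutation limit for the same mean difference, and the Hodges-Lehmann shift, as supportive results only.

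The cost is a short wording change, with no new patients or data. Under 12.2's assumptions, power at zero true difference stays at 0.907 (22 per arm) to 0.936 (25 per arm). The small downside is that the t limit is approximate with skewed data, at about 6-8% against 5%; the bootstrap or permutation limit serves as a check.

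For the error rates after the fix to apply, 17.1 must also say that scores above 7 stay in the primary analysis, and this must be reconciled with the withdrawal wording in 6.5 and 14.1. That concerns which data are analysed, not how patients are managed.
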